#### 9.4.4 Selection of Doses in the Study

In Study 304, lenvatinib had an acceptable safety profile in HCC subjects when treatment was initiated at 8 mg or 12 mg QD (based on BW) and adjusted by a dose-reduction algorithm to manage toxicity ([Study E7080-G000-304 Clinical Study Report, 2017](#)). Based

on these data, the starting dose of lenvatinib in this study will be based on baseline BW of the subjects: 12 mg QD for BW  $\geq$ 60 kg and 8 mg QD for <60 kg.

#### 9.4.5 Selection and Timing of Dose for Each Subject

Lenvatinib capsules are to be taken orally, QD in continuous 28-day cycles at approximately the same time each day in a fasting state or after a meal.

Administration of TPC should be in accordance with the approved prescribing information for the chosen treatment.

#### 9.4.6 Blinding

The study will be open label.

#### 9.4.7 Prior and Concomitant Therapy

All prior medications (including over-the-counter medications) administered 30 days before the first dose of study drug and any concomitant therapy administered to the subject during the course of the study (starting at the date of informed consent) until 28 days after last dose of lenvatinib treatment if subjects do not enter TPC period, or for 8 weeks after the start of TPC period, or up to 28 days after last dose of TPC if subject does not stay in the TPC period for the 8 weeks of safety monitoring. All anticancer therapy will be recorded until time of death or termination of survival follow-up. Additionally, all diagnostic, therapeutic, or surgical procedures relating to malignancy should be recorded. Any medication that is considered necessary for the subject's health and that is not expected to interfere with the evaluation of or interact with the study medication may be continued during the study.

Treatment of complications or AEs, or therapy to ameliorate symptoms (including blood products, blood transfusions, fluid transfusions, antibiotics, and antidiarrheal drugs), may be given at the discretion of the investigator, unless it is expected to interfere with the evaluation of (or to interact with) the study medication.

Aspirin, nonsteroidal anti-inflammatory drugs, and low-molecular-weight heparin are permissible but should be used with caution. g-CSF or equivalent may be used in accordance with American Society of Clinical Oncology (ASCO), institutional, or national guidelines. Erythropoietin may be used according to ASCO, institutional, or national guidelines, but the subject should be carefully monitored for increases in red blood cell (RBC) counts.

##### 9.4.7.1 Drug-Drug Interactions

The main metabolic pathways for lenvatinib in humans were identified as enzymatic (CYP3A and aldehyde oxidase) and non-enzymatic processes (lenvatinib – Global Investigator's Brochure).

No dose adjustment of lenvatinib is recommended when coadministered with CYP3A, PgP, and breast cancer resistance protein (BCRP) inhibitors, and with CYP3A and PgP inducers

(lenvatinib – Global Investigator’s Brochure). In a formal drug-drug interaction study, lenvatinib did not alter plasma concentrations of midazolam (a sensitive CYP3A and Pgp substrate). Thus, lenvatinib is not expected to alter the metabolism of other co-administered drugs which are CYP3A4/Pgp substrates (lenvatinib – Global Investigator’s Brochure).

A population PK analysis also indicated that agents that raise gastric pH (eg, H2-blockers, proton pump inhibitors, antacids) do not have a significant effect on the absorption and bioavailability of lenvatinib (CPMS-E7080-007R-v1).

Please refer to Flockhart DA, 2007 for the most current information regarding inhibitors and inducers of CYP3A4.

#### 9.4.7.2 Prohibited Concomitant Therapies and Drugs

The following concomitant therapies will be prohibited from the time of informed consent for this study until discontinuation from lenvatinib treatment:

- Surgery or radiotherapy for the treatment of HCC. Palliative radiotherapy of up to 2 painful pre-existing nontarget bone metastases will be permitted without being considered progressive disease (PD).
- Systemic therapy, hepatic intra-arterial chemotherapy, immunological therapy (eg, interferon, interferon-type drugs, etc), hormonal therapy, or local therapy of any kind (eg, percutaneous ethanol inject [PEI], radiofrequency ablation [RFA], TACE, etc) for the treatment of HCC. Subjects who are receiving antiviral therapy for hepatitis B virus will be allowed to continue to receive this therapy at the discretion of the investigator.
- Other investigational drugs
- Antiplatelet agents and anticoagulants that required INR monitoring, such as warfarin. (Treatments that do not require INR monitoring, such as low molecular weight heparin and certain factor X inhibitors are permitted.)

If subjects receive additional anticancer therapies, this will be judged to represent evidence of disease progression, and study medication will be discontinued. These subjects should complete all off-treatment assessments and continue to be followed for survival in the Follow-Up Period.

Drugs that are not prohibited for concomitant use include drugs used to treat complications or AEs, or drugs used to ameliorate symptoms (including blood products, blood transfusions, fluid transfusions, antibiotics, steroids, antidiarrheal drugs, and tranquilizers, etc). These drugs and treatments can be concomitantly used, based on the judgment of the investigator or subinvestigator.

#### 9.4.8 Treatment Compliance

Records of treatment compliance for each subject will be kept during the study. Clinical research associates (CRAs) will review treatment compliance during site visits and at the completion of the study.

#### 9.4.9 Drug Supplies and Accountability

In compliance with local regulatory requirements, drug supplies will not be sent to the investigator (or if regionally required, the head of the medical institution or the designated pharmacist) until the following documentation has been received by the sponsor:

- A signed and dated confidentiality agreement
- A copy of the final protocol signature page, signed and dated by both the sponsor and investigator
- Written proof of approval of the protocol, the ICFs, and any other information provided to the subjects by the IRB/IEC for the institution where the study is to be conducted
- A copy of the IRB/IEC-approved ICF and any other documentation provided to the subjects to be used in this study
- The IRB/IEC membership list and statutes or Health and Human Services Assurance number
- A copy of the certification and a table of the normal laboratory ranges for the reference laboratory conducting the clinical laboratory tests required by this protocol
- An investigator-signed and dated FDA Form FDA 1572, where applicable
- Financial Disclosure form(s) for the PI and all subinvestigators listed on Form FDA 1572, where applicable
- A signed and dated curriculum vitae (CV) of the PI including a copy of the PI's current medical license or medical registration number on the CV
- A signed and dated clinical studies agreement
- A copy of the regulatory authority approval for the country in which the study is being conducted (if required), and the Import License (if required)

The investigator and the study staff (or if regionally required, the head of the medical institution or the designated pharmacist) will be responsible for the accountability of all study drugs (dispensing, inventory, and record keeping) following the sponsor's instructions and adherence to GCP guidelines as well as local or regional requirements.

Under no circumstances will the investigator allow the study drugs to be used other than as directed by this protocol. Study drugs will not be dispensed to any individual who is not enrolled in the study other than the parent, guardian, or authorized legal representative of a study subject.

The site must maintain an accurate and timely record of the following: receipt of all study drugs, dispensing of study drugs to the subject, collection and reconciliation of unused study drugs that are either returned by the subjects or shipped to site but not dispensed to subjects, and return of reconciled study drugs to the sponsor or (where applicable) destruction of reconciled study drugs at the site. This includes, but may not be limited to:

(a) documentation of receipt of study drugs, (b) study drugs dispensing/return reconciliation log, (c) study drugs accountability log, (d) all shipping service receipts, (e) documentation of returns to the sponsor, and (f) certificates of destruction for any destruction of study drugs/study supplies that occurs at the site. All forms will be provided by the sponsor. Any comparable forms that the site wishes to use must be approved by the sponsor.

The study drugs and inventory records must be made available, upon request, for inspection by a designated representative of the sponsor or a representative of a health authority (eg, FDA, MHRA). As applicable, all unused study drugs and empty and partially empty containers from used study drugs are to be returned to the investigator (or if regionally required, the head of the medical institution or the designated pharmacist) by the subject and, together with unused study drugs that were shipped to the site but not dispensed to subjects, are to be returned to the sponsor's designated central or local depot(s) during the study or at the conclusion of the study, unless provision is made by the sponsor for destruction of study drugs and containers at the site. Approval for destruction to occur at the site must be provided by the sponsor in advance. Upon completion of drug accountability and reconciliation procedures by the site's personnel and documentation procedures by the sponsor's personnel, study drugs that are to be returned to the sponsor's designated central or local depot(s) must be boxed, sealed, and shipped back to the central or local depot(s) following all local regulatory requirements. In some regions, study drugs may be removed from the site and hand delivered to the central or local depot by sponsor representatives. Where study drugs are approved for destruction at the site, destruction will occur following the site's standard procedures and certificates of destruction will be provided to the sponsor.

Drug accountability will be reviewed during site visits and at the completion of the study.

## **9.5 Study Assessments**

### **9.5.1 Assessments**

#### **9.5.1.1 Demography**

Subject demography information will be collected during Screening. Demography information includes date of birth (or age), sex, race/ethnicity.

#### **9.5.1.2 Baseline Assessments**

Baseline assessments will be performed at Day -1 or at Cycle 1 Day 1 prior to treatment. The screening assessment can serve as the baseline assessment, if performed within 72 hours of the first dose of study treatment. Assessments will include confirmation of subject eligibility with the inclusion and exclusion criteria, medical and surgical history, prior medications and procedures, pregnancy test (serum or urine) in women of childbearing

potential within 72 hours prior to the first dose of study treatment, blood coagulation test, ECOG PS (see [Appendix 5](#)), Child-Pugh score (see [Appendix 4](#)), vital signs and weight, clinical chemistry and hematology, and urine dipstick testing.

#### 9.5.1.2.1 MEDICAL HISTORY AND PHYSICAL EXAMINATIONS

Medical and surgical history and current medical conditions will be recorded at the Screening and Baseline Visits. All medical and surgical history must be noted in the Medical History and Current Medical Conditions CRF.

Physical examinations (comprehensive or symptom directed) will be performed as designated in the Schedule of Assessments ([Table 3](#)). A comprehensive physical examination will include evaluations of the head, eyes, ears, nose, throat, neck, chest (including heart and lungs), abdomen, limbs, skin, and a complete neurological examination. Documentation of the physical examination will be included in the source documentation at the site. Significant findings at screening will be recorded on the Medical History and Current Medical Conditions CRF. Changes from screening physical examination findings that meet the definition of an AE will be recorded on the Adverse Events CRF.

#### 9.5.1.3 Efficacy Assessments

All efficacy endpoints, other than OS, will be based on the tumor response evaluation as determined by investigator assessment according to mRECIST (and including the RECIST 1.1 conventions for non-hepatic lesions). Tumor assessments will be performed at the site by appropriately qualified personnel. Treatment decisions will be based on tumor response assessments determined by the investigator.

##### 9.5.1.3.1 TUMOR ASSESSMENTS

Tumor assessments will be performed during the Screening/Baseline phase (standard of care scans performed up to 28 days before the first dose of study treatment are acceptable) and then every 8 weeks ( $\pm 1$  week), or sooner if clinically indicated, during the Lenvatinib Treatment Period until disease progression ([Table 3](#)).

Subjects who discontinue lenvatinib treatment without disease progression should have tumor assessments performed (within 1 week of the lenvatinib Off-Treatment Visit) if more than 4 weeks have passed since the previous assessment and if the subject will not continue with follow-up scans.

Subjects entering the subsequent TPC period should have TPC baseline tumor assessments performed unless the last tumor assessment performed in the Lenvatinib Treatment Period is less than 28 days before the subsequent treatment starts, in which case those scans may be used as the TPC period baseline. A new tumor assessment baseline (selection of target and non-target lesions and calculation of a new baseline sum of diameters (SOD) must be established before beginning TPC. Subjects will continue tumor assessments during the subsequent TPC period every 8 weeks ( $\pm 1$  week), or until disease progression, subject death, withdrawal or loss to follow-up.

Tumor assessments will utilize mRECIST based on Lencioni and Llovet ([Appendix 2, Lencioni and Llovet, 2010](#)). Copies of all tumor imaging scans will be sent to an imaging core laboratory designated by the sponsor for potential future review. All subjects are required to undergo chest, abdomen, and pelvis imaging at baseline and all follow-up time points. Contrast-enhanced CT of the chest and contrast-enhanced CT or MRI of the abdomen, pelvis, and any other areas of disease, as clinically indicated, will be acquired at Screening and at all imaging time points. Liver CT or MRI must be performed using triphasic scanning technique optimized to capture precontrast, arterial and portal venous phase.

Screening tumor assessments using triphasic liver CT/MRI (optimized for pre-contrast, arterial phase, and portal venous phase), contrast-enhanced CT of the chest, and contrast-enhanced CT or MRI of abdomen, pelvis, and other areas of known disease plus suspected disease should be performed within 28 days prior to treatment.

Screening CT of the brain with contrast or MRI of the brain pre- and post-gadolinium should be performed within 28 days prior to treatment. During the Treatment Phase, CT/MRI of the brain should be performed if clinically indicated. The same methodology and scan acquisition techniques used at Screening should be used throughout the study to ensure comparability.

During the Treatment Phase, tumor assessments using triphasic liver CT/MRI (optimized for pre-contrast, arterial phase, and portal venous phase), contrast-enhanced CT of the chest and contrast-enhanced CT or MRI of the abdomen, pelvis, and other areas of known disease at Screening plus newly suspected disease should be performed every 8 weeks (during the eighth week; starting from the date of the first treatment of lenvatinib), or sooner, if clinically indicated. The same methodology (CT or MRI) and scan acquisition techniques, including use and timing of IV contrast, should be used as for the screening assessments. Tumor assessment at the lenvatinib Off-Treatment Visit is only necessary if more than 4 weeks have passed since the previous assessment (window for these assessments is within 1 week of the lenvatinib Off-Treatment Visit).

If a subject discontinues from the study prior to the Week 8 scan, then a CT/MRI scan should be performed as close as possible to 8 weeks after treatment. If a subject discontinues prior to Week 8, the scans for tumor assessment should be performed as close as possible to Week 8 but before another anticancer therapy is initiated.

Target lesions in bone may not receive palliative radiotherapy. A maximum of 2 bone metastases that become painful and are being followed as bone non-target lesions on CT or MRI scans (using bone windows/sequences) may be treated with palliative radiotherapy. The lesion(s) should be considered as not evaluable (NE) for all subsequent time points, unless they later progress unequivocally.

If a subject is unable to undergo a contrast CT due to allergy or renal insufficiency during follow-up, a chest CT without contrast, combined with MRI images of the remaining anatomy with gadolinium contrast, is preferred if tolerated by the subject. If it is determined

that neither CT nor MRI IV contrast can be tolerated by the subject during follow-up, a chest CT without contrast combined with high quality T1 and T2 weighted MRI images of the remaining anatomy should be provided. Importantly, such a modality switch will render the subsequent measurements of target lesions, especially typical hepatic target lesions, inadequate and the target lesion disease should be followed as NE or potentially progressing (if sufficient evidence is available).

The tumor assessment schedule should not be affected by interruptions in therapy, or any other events that might lead to imbalance between the treatment groups with regard to the timing of disease assessments.

CT and MRI scans should be of diagnostic quality acquired on spiral or multidetector CT with oral and IV contrast. Low dose noncontrast CT transmission scans from positron emission tomography (PET)/CT scanner are not acceptable. Spiral or multidetector CT should be performed with a 5 mm contiguous slice reconstruction algorithm. If MRI scans are acquired, contiguous 5 mm slice thickness with minimal gap are also recommended. Ultrasound should not be used for radiographic assessment. A chest x-ray that clearly demonstrates a new metastatic lesion may be used to document progression in lieu of the CT/MRI scans.

Brain scans should be performed by MRI pre- and post-contrast enhancement or CT with contrast enhancement, with 5-mm contiguous slices recommended (maximum inter-slice gap of 1 mm on MRI).

In order to be eligible for this study, all subjects must have at least one measurable lesion visible on screening CT or MRI scans. To adequately determine lesion progression and response, the investigator will categorize the baseline disease burden on the screening image into typical, atypical, and nonhepatic target and nontarget lesions. Lesions previously treated with radiotherapy or surgical therapy should not be considered suitable as target lesions, unless they show radiographic evidence of disease progression. The investigator will follow each of the selected lesions at each subsequent imaging time point until radiological progression is determined. If a lesion that was not present at baseline is detected on a follow-up scan, it will be identified as a new lesion. At every time point, the investigator will determine the overall tumor response of a subject as CR, PR, stable disease (SD), NE, or PD, as appropriate (see [Appendix 2](#) for further details).

#### 9.5.1.4 Pharmacokinetic, Pharmacodynamic, Pharmacogenomic, and Other Biomarker Assessments

##### 9.5.1.4.1 PHARMACOKINETIC ASSESSMENTS

Not applicable.

#### 9.5.1.4.2 PHARMACODYNAMIC, PHARMACOGENOMIC, AND OTHER BIOMARKER, ASSESSMENTS

##### **Pharmacodynamic Blood Biomarkers**

Blood serum samples for pharmacodynamic and exploratory biomarkers analysis will be collected at the following time points:

Treatment Period 1: Before dosing (predose) lenvatinib on Cycle 1 Day 1, Cycle 1 Day 15, Day 1 of all subsequent cycles, and at the off-treatment assessment.

Treatment Period 2: Subjects entering the subsequent TPC period should have TPC baseline sample collected unless the lenvatinib Off-Treatment visit in the lenvatinib treatment period is  $\leq 28$  days before the subsequent treatment starts, in which case those samples may be used as the TPC period baseline. Samples will then be collected at week 8 and week 16 ( $\pm 1$  week).

A detailed biomarker analysis plan will be prepared separately.

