#### 9.1.2.1 Lenvatinib Treatment Period (Treatment Period 1)

Lenvatinib Treatment Period for each subject will begin with the administration of first dose of lenvatinib on Cycle 1 Day 1 and will consist of administration of lenvatinib in 28-day treatment cycles. Treatment Period 1 will continue until completion of the lenvatinib Off-Treatment Visit that will occur within 30 days after the final administration of lenvatinib.

Lenvatinib treatment cycles will be counted continuously regardless of dose interruptions. Subjects will undergo safety and efficacy assessments as defined in the Schedule of Procedures/Assessments ([Table 3](#)). Subjects will continue to receive study treatment until disease progression, development of unacceptable toxicity, subject request, withdrawal of consent, or study termination by the sponsor.

Subjects will be permitted to continue lenvatinib treatment beyond mRECIST defined disease progression as long as the treating investigator considers that there is clinical benefit and, the subject is tolerating study treatment. The assessment of clinical benefit should take into account whether the subject is clinically deteriorating and unlikely to receive further benefit from continued treatment. All decisions to continue treatment beyond initial progression must be discussed with the Eisai Medical Monitor. Subjects will discontinue study treatment upon evidence of further progression and/or loss of clinical benefit, as judged by the investigator.

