#### 9.1.2.2 Subsequent Treatment Period (TPC Period, Treatment Period 2)

The subsequent TPC period will begin upon the completion of the lenvatinib Off-Treatment Visit in first-line treatment of lenvatinib. Subjects will be treated with commercially available systemic TPC for uHCC. The first treatment of a single agent or combination of multiple drugs after lenvatinib treatment will be considered as the subsequent TPC. Locoregional therapies (ie, chemoembolization/radioembolization, etc) procedures will not

be considered as a second line treatment following lenvatinib. If the investigator deems a subject inappropriate for commercially available systemic TPC as the subsequent treatment following lenvatinib, subjects will be followed in the survival Follow-Up period. All treatment following lenvatinib will be captured in the case report form. Data will be collected from the start of TPC, then at intervals as indicated in Schedule of Procedures/Assessments ([Table 3](#)).

Subjects starting subsequent TPC  $\geq$ 8 weeks after lenvatinib off-treatment visit may be considered after discussion with sponsor.

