- n: Clinical laboratory tests (hematology and clinical chemistry) will be performed at local laboratory. Laboratory tests at Baseline may be performed up to 72 hours prior to first dose of lenvatinib treatment. Review hematology clinical chemistry results within 48 hours after receiving quick estimation. Assessments scheduled may be performed within 72 hours prior to the visit. If  $\geq$  Grade 3 hematologic or clinical chemistry toxicities, repeat laboratory test and AE assessment at least every 7 days (until improvement to  $<$ Grade 3). Clinical laboratory tests will be performed at week 2, week 4, and week 8 ( $\pm 1$  week) in TPC period. A TPC baseline assessment should be performed unless the lenvatinib Off-Treatment visit is completed  $\leq 7$  days prior to the first TPC treatment.
- o: For subjects with proteinuria  $\geq 2+$  (see the dose adjustment table for management of proteinuria).
- p: A serum or urine pregnancy test will be performed in women of childbearing potential (ie, premenopausal women and postmenopausal women who have been amenorrheic for less than 12 months). A separate baseline assessment is required if a negative screening pregnancy test was obtained more than 72 hours before the first dose of study drug.
- q: PRO-CTCAE data will be collected at the following time points: lenvatinib Off-Treatment Visit during Treatment Period 1, every 2 weeks for the first 4 weeks, and then at week 8 and week 16 ( $\pm 1$  week) in Treatment Period 2. A TPC baseline assessment should be performed unless the lenvatinib Off-Treatment visit is completed  $\leq 7$  days prior to the first TPC treatment.
- r:  $\alpha$ -Fetoprotein (AFP) and thyroid-stimulation hormone (TSH) will be measured at screening visit, Baseline, on C1D15, C2D1, C3D1, and every 2 cycles thereafter (C5D1, C7D1, C9D1, etc) in Treatment Period 1, and week 8 and week 16 ( $\pm 1$  week) in TPC period. A TPC baseline assessment should be performed unless the lenvatinib Off-Treatment visit is completed  $\leq 7$  days prior to the first TPC treatment.

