- s: Collection of blood sample to obtain serum and plasma to be used for biomarker studies. Samples will be obtained on C1D1 (predose), predose on C1D15, Day 1 of and all subsequent cycles, and the lenvatinib Off-Treatment Visit in Treatment Period 1, and at week 8 and week 16 ( $\pm 1$  week) in Treatment Period 2 (TPC period). A TPC baseline assessment should be performed unless the lenvatinib Off-Treatment visit in Treatment Period 1 is  $\leq 28$  days before the first TPC treatment. A whole blood sample for genetic analysis will be obtained at baseline. If sampling is not performed predose, sampling may occur at any subsequent visit in which other blood sampling is scheduled to occur.
- t: Screening Period: Tumor assessments using triphasic liver CT/MRI (optimized for precontrast, arterial phase and portal venous phase), contrast-enhanced CT of the chest, and contrast-enhanced CT or MRI of the abdomen, pelvis, and other areas of known disease plus suspected disease should be performed within 28 days prior to first dose of study treatment.  
Treatment Period: Tumor assessments using triphasic liver CT/MRI (optimized for precontrast, arterial phase and portal venous phase), contrast-enhanced CT of the chest, and contrast-enhanced CT or MRI of the abdomen, pelvis, and other areas of known disease at screening or newly suspected disease should be performed every 8 weeks (during the 8th week) ( $\pm 1$  week) or sooner if there is evidence of progressive disease. The same methodology (CT or MRI) and scan acquisition techniques should be used as for the screening assessments.  
Tumor assessments will be performed during the Screening/Baseline Phase (standard of care scans performed up to 28 days before the first dose of study treatment are acceptable) and then every 8 weeks, or sooner if clinically indicated, during lenvatinib treatment phase until disease progression. Subjects

who discontinue lenvatinib treatment without disease progression should have tumor assessments performed (within one week of the lenvatinib Off-Treatment Visit) if more than 4 weeks have passed since the previous assessment and if the subject will not continue with follow-up scans.

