#### **9.7.1.7.2 PHARMACODYNAMIC, PHARMACOGENOMIC, AND OTHER BIOMARKER ANALYSES**

The effect of study treatment on soluble, tissue, genetic and/or other relevant biomarkers will be summarized using descriptive statistics using the Pharmacodynamic Analysis Set and correlated with clinical outcomes-related endpoints for safety and/or efficacy as appropriate. Details will be included in a separate analysis plan.

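### The TPC biomarker baseline may be a lenvatinib Off-Treatment sample up to 28 days old, so for some subjects the Week 8 and Week 16 changes mix lenvatinib washout with any TPC effect

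*Combined protocol and SAP*

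**What the plan says.** The serum rule is in the Synopsis and Section 9.5.1.4.2. A subject entering the TPC period has a new baseline sample unless the Off-Treatment Visit was at most 28 "days before the subsequent treatment starts, in which case those samples may be used as the TPC period baseline". The same sections apply the rule to plasma for cell-free nucleic acids. Table 3, footnote s, agrees: "A TPC baseline assessment should be performed unless the lenvatinib Off-Treatment visit in Treatment Period 1 is" 28 days or less before the first TPC treatment. After baseline, "Samples will then be collected at week 8 and week 16", with a window of one week.

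Section 9.1.2.1 ends Treatment Period 1 with "completion of the lenvatinib Off-Treatment Visit that will occur within 30 days after the final administration of lenvatinib". No minimum interval is given. Section 9.1.2.2 adds none: "The subsequent TPC period will begin upon the completion of the lenvatinib Off-Treatment" Visit.

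Elsewhere in Table 3 the limit is 7 days. "A TPC baseline assessment should be performed unless the lenvatinib Off-Treatment visit is completed" no more than 7 days before the first TPC treatment is the rule for vital signs (footnote h), physical examination (j), ECG (l), hematology and chemistry (n), PRO-CTCAE (q) and AFP/TSH (r). Footnotes d and i set the same limit for ECOG, Child-Pugh and urine dipstick. Tumor imaging is the exception: Section 9.5.1.3.1 and footnote t accept lenvatinib-period scans less than 28 days old.

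On analysis, Section 9.7.1.7.2 says: "The effect of study treatment on soluble, tissue, genetic and/or other relevant biomarkers will be summarized using descriptive statistics". Results are also to be correlated with outcomes, with details left to a separate plan that is not among the documents.

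**The concern.** A baseline for a second treatment period should describe the subject just before that treatment begins. Here one subject's TPC baseline may be drawn on the day of the last lenvatinib dose and another's after 30 drug-free days. Either sample may then age up to 28 days before TPC starts. The next samples come at Weeks 8 and 16, so nothing in between separates the reversal of a lenvatinib effect from the onset of a TPC effect.

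At stake is the reading of Period 2 biomarker change. Appendix 9 seeks markers that predict response to lenvatinib and to the subsequent treatment, so the two periods are meant to be told apart. A marker that lenvatinib shifts would appear to move under TPC simply because lenvatinib was stopped, and by an amount that depends on each subject's visit timing.

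**Working it through.** The plan states no figure on this point, so there is none to reproduce. The check adds up the protocol's windows and then illustrates the consequence under labelled assumptions.

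**Inputs from the protocol**
- Last lenvatinib dose to Off-Treatment sample, *a*: 0 to 30 days (Section 9.1.2.1).
- Off-Treatment sample to TPC start when the sample is carried forward, *g*: 0 to 28 days (Section 9.5.1.4.2; footnote s).
- Week 8 = day 56 ± 7 and Week 16 = day 112 ± 7, counted from TPC start.

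**Intervals**
- Last dose to TPC start with a carried sample, *a* + *g*: 0 to 30 + 28 = 58 days.
- Sample to Week 8, *g* + 56 ± 7: 49 to 28 + 63 = 91 days. With a 7-day limit: 49 to 7 + 63 = 70. With a sample on the day TPC starts: 49 to 63.
- Sample to Week 16, *g* + 112 ± 7: 105 to 28 + 119 = 147 days. With a 7-day limit: 105 to 126. With a same-day sample: 105 to 119.

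The 58-day maximum holds only for carried samples. Section 9.1.2.2 allows TPC to be considered at 8 weeks or more after the Off-Treatment Visit, and such subjects need a fresh sample.

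**Illustration (assumed kinetics)**

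Suppose the lenvatinib effect on a marker decays as *r*(*t*) = 0.5^(*t*/*h*) after the last dose, with half-life *h* of 1, 3, 7 or 14 days. The form and the half-lives are assumptions. The washout contained in the change to day 56 of TPC, as a share of the full lenvatinib effect, is:
- carried sample: *r*(*a*) − *r*(*a* + *g* + 56)
- sample drawn on the day TPC starts: *r*(*a* + *g*) − *r*(*a* + *g* + 56)

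For *h* = 14, *a* = 0, *g* = 28: carried 1 − 0.5^6 = 0.98; fresh 0.25 − 0.5^6 = 0.23.

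Ranges over the four half-lives:

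| *a* (days) | *g* (days) | Carried sample | Fresh sample |
|---|---|---|---|
| 0 | 0 | 0.94–1.00 | 0.94–1.00 |
| 0 | 7 | 0.96–1.00 | 0.01–0.66 |
| 0 | 28 | 0.98–1.00 | 0.00–0.23 |
| 7 | 28 | 0.01–0.70 | 0.00–0.17 |
| 14 | 14 | 0.00–0.48 | 0.00–0.23 |
| 30 | 0 | 0.00–0.21 | 0.00–0.21 |
| 30 | 28 | 0.00–0.22 | 0.00–0.05 |

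The mixing is large when the sample is drawn close to the last dose and small when it is drawn near day 30. A fresh sample helps when the first interval is short and the second long. It does nothing when TPC starts on the last-dose day. At gaps of 7 days or less, a 7-day rule would still allow the carried sample, so the second row's carried value would remain possible.

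**The case against.** The strongest reply is that the plan defines no change from TPC baseline. The biomarker analysis is descriptive, the carry-forward is permissive, and the separate biomarker plan may choose another reference or adjust for timing. Cycle 1 Day 1 and per-cycle samples are also available. Section 9.7.1.2 requires a documented dosing history for the Pharmacodynamic Analysis Set, so days since the last lenvatinib dose can already be derived. Much of this stands. It limits the point but does not remove it: naming a sample the period baseline invites that comparison, and no analysis plan can recover a pre-TPC sample that was never drawn.

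A reader might infer more than the documents support:
- *That biomarkers alone get the long window.* Tumor imaging has nearly the same one. The contrast is with the laboratory, clinical and patient-reported assessments.
- *That these are the samples most sensitive to lenvatinib.* No marker is named, and blood pressure and proteinuria, which the protocol manages as lenvatinib effects, are under the 7-day rule.
- *That no Period 2 change can be attributed to TPC.* The problem depends on timing and is small for samples taken well after the last dose.
- *That the gap follows the reason lenvatinib was stopped.* This is plausible, but nothing in the documents shows it.
- *That a 7-day rule cures the problem.* It does not when TPC follows the last dose closely, because part of the mixing comes from giving the treatments in sequence with no stated minimum interval.

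**Conclusion.** The point holds as a minor design weakness. It concerns subjects whose Off-Treatment sample is drawn soon after the last lenvatinib dose and who start TPC 8 to 28 days later. For them the carry-forward rule allows a baseline that a fresh draw would improve, and a change from it to Week 8 or 16 mixes washout with any TPC effect.

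The size in marker units cannot be derived from the documents. The shares in the working rest on assumed exponential decay and assumed half-lives of 1 to 14 days, and the number of subjects in this position is unknown. The conclusion also assumes that the sample called the TPC baseline will be used as one.

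Only the exploratory biomarker objective (Section 8.3) is affected. The primary safety endpoint, OS, PFS, TTP, PRO-CTCAE and the sample size are untouched.

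**What to change.** 1. In the Synopsis and Section 9.5.1.4.2 (serum and plasma paragraphs) and in Table 3, footnote s, replace the 28-day limit with the 7-day limit used for the other TPC-baseline laboratory assessments. When the gap exceeds 7 days, footnotes n and r already require a TPC-baseline blood draw for hematology, chemistry and AFP/TSH. The serum and plasma tubes can be added to that draw, before the first TPC dose.

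2. In the separate biomarker plan, derive two intervals from the dosing history: last lenvatinib dose to baseline sample, and last lenvatinib dose to TPC start. Present Period 2 biomarker change by these intervals. This is needed as well as the first change, which leaves washout in place when TPC starts within days of the last lenvatinib dose.

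The cost is a few more samples to process and a written wording change under Section 11.1, communicated to the 20 to 25 sites. No extra visit or venipuncture is needed, and the second step needs no new dosing data.
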